# **12 SAFETY MONITORING**

## 12.1 Adverse Event and Serious Adverse Event Recording and Reporting

All AEs/SAEs (except non-serious AEs for screening failures) that occur after the signing of informed consent and up to the End of Study visit (or up to 28 days after the last administration of study medication, whichever is earlier), will be recorded in the eCRF and in the subject's medical records, whether or not considered by the investigator to be related to the study drug. The SAEs should thereafter be recorded in the SAE Report Form and reported to the sponsor. All AEs/SAEs should be recorded using acceptable diagnoses, if possible. For screening failure subjects the non-serious AEs will not be recorded in the eCRF but only in the subject's medical records. The SAEs for screening failures will only be recorded until (including) the day when a subject is officially declared as screening failure.

Infusion reactions of grade 3 and higher, cytokine release syndrome, or allergic reaction to MOR03087, which are AEs of special interest in this study, should be reported along with their respective symptoms (e.g., urticaria, chills, and pyrexia for infusion reaction). If an AE has already been reported, it is not necessary to report each individual sign and symptom of that AE as a separate AE. For example, if myocardial infarction is reported as an AE, there is no need to report elevated creatine phosphokinase and abnormal ECG, or other related signs, symptoms, or laboratory values as separate AEs. However, if both occurred in isolation and myocardial infarction was not diagnosed, then each event would be reported as an AE.

Second primary malignancies will be monitored as events of special interest regardless of the treatment arm the subject is in. This includes any second primary malignancy, regardless of causal relationship to IP occurring at any time for the duration of the study. Events of second primary malignancy are to be reported using the SAE report form and must be considered an "Important Medical Event" if no other serious criteria apply. Documentation on the diagnosis of the second primary malignancy must be provided at the time of reporting (e.g., any confirmatory histology or cytology results, x-rays, CT scans, etc.).

The intensity of all AEs will be graded as mild, moderate, or severe using the following definitions:

- Mild: Tolerable
- Moderate: Interferes with normal activity
- Severe: Incapacitating (causes inability to perform usual activity or work)

The toxicity grade of AEs will be graded according to the NCI CTCAE (version 4.0 of May 28, 2009) using the following definitions:

- Grade 1: Mild; asymptomatic or mild symptoms; clinical or diagnostic observations only; intervention not indicated.
- Grade 2: Moderate; minimal, local or non-invasive intervention indicated; limiting age-appropriate instrumental activities of daily living (refers to

preparing meals, shopping for groceries or clothes, using the telephone, managing money, etc.).

- Grade 3: Severe or medically significant but not immediately life-threatening; hospitalization or prolongation of hospitalization indicated; disabling; limiting self-care activities of daily living.
- Grade 4: Life-threatening consequences; urgent intervention indicated.
- Grade 5: Death related to AE.

The causal relationship of all AEs to IMP intake will be judged as either suspected or not suspected. If no relationship has been provided by the investigator, the event will be considered as related to study drug and notified to authorities according to regulatory reporting requirements.

In addition to the investigator's own description of the AEs, each AE will be encoded by the sponsor (or its delegate) according to the current version of the Medical Dictionary for Regulatory Activities (MedDRA).

All non-serious AEs must be followed up for a final outcome until resolution or until the EOS visit. An outcome of "unknown" is not considered to be an acceptable final outcome. An outcome of "not yet resolved" is an acceptable final outcome for non-serious AEs at the end of a subject's participation in a study. SAEs must be followed up for a final outcome until resolution or, if resolution becomes unlikely, until stabilization or death. This includes obtaining information on recovery and any sequelae and, in case of a fatal outcome, the cause of death. For SAEs which are due to progression of MM, follow-up only until the end of subject's participation in the study is acceptable.

will report all reportable events to all competent authorities (including the European Medicines Agency [EMA]), IECs or Institutional/Independent Review Boards (IRBs), and investigators as required by local regulations and Premier Research standard operating procedures (SOPs).

Sites are instructed to report all SAEs and AEs of special interest (i.e., infusion reactions of grade 3 and higher, cytokine release syndrome, allergic reaction to MOR03087, second primary malignancies and DLTs) to within 24 hours using the study-specific SAE report form.

Notification of initial or follow-up SAE information (using the standard SAE form provided by the sponsor) must be sent to the attention of Global Pharmacovigilance using either the following email address or fax number:

Email:	
Fax:	
For any safety-related questions, please contact telephone, fax or email:	Global Pharmacovigilance by

Sponsor: MorphoSys AG

For any protocol-related questions, please contact the medical monitor:
If the medical monitor cannot be reached, then please contact the following 24/7 emergency medical cover phone line: Telephone:
If the medical monitor cannot be reached, then the following person should be contacted:
As detailed in the schedules of assessments (Section 7.1) and Section 11.3.4, serum or urine pregnancy testing will be carried out at the Screening visit, during treatment, during follow-up visits, and at the EOS visit. During the treatment period of the study, urine pregnancy testing will be performed locally and can be repeated if required. Any pregnancy that occurs during study participation should be reported using a Clinical Study Pregnancy Form. To ensure subject safety, each pregnancy of a study subject or a female partner of a study subject must also be reported within 24 hours of learning of its occurrence to

Fax:	

Female study subjects who become pregnant must be withdrawn from the study.

Pharmacovigilance by fax at the following number:

A newly diagnosed pregnancy in a subject or female partner of a study subject who has received study medication is not considered an SAE unless it meets any criteria of seriousness or it is suspected that the study medication interacted with a contraceptive method and led to pregnancy.

Sponsor: MorphoSys AG

The pregnancy should be followed up to determine outcome, including spontaneous or voluntary termination, details of birth, and the presence or absence of any birth defects or congenital abnormalities or maternal and newborn complications. Every infant has to be followed up for 2 months after delivery.

Cohorts with POM or LEN administration:

**Pregnancy Counseling (males and females):** Counseling about pregnancy precautions and the potential risks of fetal exposure must be conducted for all subjects at screening, at Cycle 1 Day 1 prior to dosing, every 28 days during treatment, and at treatment discontinuation. Refer to Appendix 18.8 (pregnancy prevention risk minimization plan).

**Pregnancy Testing for Females of Childbearing Potential (FCBP):** All FCBP must have two medically supervised negative serum or urine pregnancy tests (sensitivity of at least 25 mIU/mL) prior to starting the study. The first pregnancy test must be performed within 10-14 days prior to the start of study treatment and the second pregnancy test must be performed within 24 hours prior to the start of study treatment. FCBP with regular or no menstrual cycles must agree to have pregnancy tests every 7 days (weekly) for the first 4 weeks of study treatment and then every 4 weeks while on study, at treatment discontinuation, and 4 weeks following treatment discontinuation. If menstrual cycles are irregular, the pregnancy testing must occur weekly for the first 4 weeks and then every 2 weeks while on study, at treatment discontinuation. Study drug may not be dispensed for FCBP until the investigator has verified that the result of the pregnancy test is negative.

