Cohort expansion up to 6 subjects will be allowed if a dose limiting toxicity (DLT) (as defined in Section 8.5) is observed in 1 of 3 subjects. If 2 or 3 subjects experience a DLT in cohorts 6b or 6c, the study sponsor may decide to test a lower dose. If 2 or 3 subjects of the 3 subjects in any of the other cohorts experience DLT, then the previous cohort should be expanded to 6 subjects.

A pharmacokinetic interim analysis may be performed at any time during dose escalation if unexpected MOR03087 serum concentration results are observed. The rationale for performing the pharmacokinetic interim analysis is to verify whether the derived pharmacokinetic parameters from this interim analysis (e.g., C_{max} , AUC, terminal elimination half-life, etc.) are still within the expected range. If there are major deviations from the expected values, it may be considered necessary to investigate a further dosing regimen or to expand the dose escalation including further cohorts via a substantial amendment to the protocol.

After study drug discontinuation due to reason other than disease progression, all subjects will return for a follow-up visit 1 and follow-up visit 2. Further follow-up visits will be conducted at 4-week intervals until the subject is progressive, begins subsequent anti-myeloma therapy, or dies.

All subjects will be followed up for a maximum of 3 years after first administration of study drug.

Study visits will be conducted according to the Schedules of Assessments provided in Table 1 (for subjects receiving bi-weekly MOR03087 treatment) and Table 2 (for subjects receiving weekly/bi-weekly MOR03087 treatment).

]	Freatme	nt (Tx) C	Cycle 1 (I	Days 1-28	8)	Тх	Cycle 2	(Days 29	-56)	Tx Cycles 3+	Follow-up	Follow-up Visit 2	EOS Visit ²
Evaluation or Procedure	Screening (≤ 4 weeks before Day 1)	D1	D2	D4	D8 ± 1 day	D15 ±1 day	D22 ±1 day	D29 C2D1 ±1 day	D36 C2D8 ± 1 day	D43 C2D15 ± 1 day	D50 C2D22 ± 1 day	Visit: repeated bi- weekly (± 2 days)	Visit 1 (4 weeks ± 2 days after last dose)	(4 weeks ± 2 days after Follow-up Visit 1) ¹	
Informed consent	X														
Medical history ³	X														
Demography	X														
Inclusion/exclusion criteria	X	X ⁴													
Karnofsky performance status	X	X ⁴								X4		X^5	Х	Х	Х
Premedication		X ⁶		X ⁶		X ⁶		X ⁶		X ⁶		X ⁶			
Study drug administration (2-hour infusion)		Х		X		Х		X		X		Х			
Laboratory															
"Emergency laboratory"7		X ⁸		X8		X ⁸		X8		X8		X			

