#### Follow-Up Visit 2 and Subsequent Follow-Up Visits:

Four weeks ( $\pm 2$  days) after Follow-up Visit 1, a second follow-up visit will occur. If there is still a response to therapy at this visit, then a follow-up visit will be repeated every fourth week ( $\pm 2$  days) until there is a disease progression (but no longer than 3 years), death, or the subject starts a new anti-myeloma therapy. Follow-up visits may be delayed for a maximum of 2 weeks after the normal visit window due to other reasons (e.g., logistical).

At each of these visits, the following will be obtained, performed, or assessed:

- Toxicity/AE assessment since the last visit
- Concomitant medication
- Karnofsky performance status
- Blood sample for hematology, serum chemistry, βHCG pregnancy test for women of childbearing potential, anti-MOR03087 antibodies (at Follow-up Visit 2 only), B, T, and NK cells, serum M-protein, and serum FLCs
- Sample from 24-hour urine for urine M-protein
- Response assessment, to be continued until disease progression or death or subsequent anti MM therapy start whatever occurs first. Note: all responses require two consecutive assessments, and should ideally be confirmed at the next follow-up visit.
- Physical examination (including basic neurological examination of general motor and sensory systems, mental status, cranial nerves, and coordination)
- Body weight
- Quality of life questionnaires (QLQ-MY20 and QLQ-C30)
- 12-Lead ECG, if clinically indicated at the discretion of the investigator
- Vital signs (blood pressure, pulse rate, respiratory rate, and body temperature)
- Clinical review of signs/symptoms for possible VTEs in subjects treated with POM or LEN. Subjects who develop symptomatic deep vein thrombosis will be assessed and diagnosed objectively by Doppler ultrasonography or a comparable method per institution's standard of care. See Appendix 18.9 for deep vein thrombosis and pulmonary embolism diagnostic algorithms

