## 10.1.14 End of Study (EOS) Visit

The EOS visit will occur after confirmed disease progression, or after withdrawal from the study for other reasons, or at a maximum of 3 years from the first study drug administration. The EOS visit will occur at least 28 days after last study drug administration but should be performed before any new MM therapy starts, whichever occurs first.

At the EOS visit, the following will be obtained, performed, or assessed:

- Toxicity/AE assessment since the last visit
- Concomitant medications
- Karnofsky performance status
- Blood sample for hematology, serum chemistry, coagulation, βHCG pregnancy test for women of childbearing potential, MOR03087 pharmacokinetics (only if subject had no follow-up visit), endocrinology, anti-MOR03087 antibodies, B, T, and NK cells, serum M-protein, and serum FLCs
- Urine sample for urinalysis
- Sample from 24-hour urine for urine M-protein
- Bone skeletal survey by x-ray, CT, or MRI imaging (where medically indicated, as a regular assessment of standard of care in subjects with relapsed or refractory MM)
- Response assessment
- Physical examination (including basic neurological examination of general motor and sensory systems, mental status, cranial nerves, and coordination)
- Ocular examination by an ophthalmologist (including distance visual acuity, optical coherence tomography [if available], and ophthalmoscopy under full mydriasis [if optical coherence tomography is unavailable])
- Body weight
- Quality of life questionnaires (QLQ-MY20 and QLQ-C30)
- 12-Lead ECG
- Vital signs (blood pressure, pulse rate, respiratory rate, and body temperature)
- Documentation of subject's subsequent anti-myeloma therapy, as appropriate

For subjects receiving POM or LEN, the additional following will be obtained, performed, or assessed:

• Clinical review of signs/symptoms for possible VTEs in subjects treated with POM or LEN. Subjects who develop symptomatic deep vein thrombosis will be assessed and diagnosed objectively by Doppler ultrasonography or a comparable method per institution's standard of care. See Appendix 18.9 for deep vein thrombosis and pulmonary embolism diagnostic algorithms

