## **11.3 Safety Assessments**

Safety monitoring for all subjects enrolled in the study will include laboratory safety assessments (hematology, blood and urine chemistry) and clinical evaluations (physical examinations, vital signs, 12-lead ECG) as detailed in the schedules of assessments (Section 7.1) and Section 11.3.4. All AEs and serious AEs (SAEs) will be recorded.

All AEs and SAEs will be graded according to NCI CTCAE, version 4.0. For definition of DLTs, please refer to Section 8.5.

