## 11.3.1 Adverse Events

Study personnel must remain vigilant for the occurrence of AEs, particularly those that may be life-threatening. Personnel who are trained in the acute management of infusion reactions, anaphylaxis, and other emergencies and who have access to appropriate clinical supplies must be immediately available for no less than 30 minutes after dosing.

An AE is defined as the appearance of (or worsening of any pre-existing) undesirable sign(s), symptom(s), or medical condition(s) occurring after signing the informed consent even if the event is not considered to be related to the study drug(s). Please refer to Sections 9 and 10 for the protocol-specific definitions of study drug and study treatment. An AE can therefore be any unfavorable and unintended sign, symptom, or disease temporally associated with the use of an IMP, whether or not considered related to that IMP. AEs include any clinically significant deterioration of a subject's medical status after signing of the informed consent form.

Any abnormal laboratory value judged to be clinically significant is defined as AE.

The subjects will be closely observed and questioned for any kind of AE during the study procedures and at follow-up appointments throughout the study period with non-leading questioning (e.g., "How do you feel?"). AEs also may be detected when they are volunteered by the subject during or between study visits or through physical examination, laboratory tests, or other assessments. As far as possible, each AE should be evaluated to determine the following:

- Relationship to study drug (suspected/not suspected)
- Duration (start and end date or if continuing at end of study)
- Intensity
- Toxicity grade
- Outcome
- Action taken (no action taken; dose reduction; study drug temporarily interrupted; study drug permanently discontinued due to this adverse event; concomitant medication taken; non-drug therapy given; hospitalization/prolonged hospitalization)
- Whether it is serious, where a serious adverse event (SAE) is defined as one which:
  - Results in death.
  - Is life-threatening.
  - Requires inpatient hospitalization or prolongation of existing hospitalization, unless hospitalization is for
    - Routine treatment or monitoring of the studied indication, not associated with deterioration of symptoms related to MM

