10.2 Adverse Events

All TEAEs and SAEs will be coded using MedDRA (MedDRA Version 20.1, and updated to the newest version 23.0 for the follow-up analyses).

The body systems 'Blood and lymphatic system disorders' and 'Investigations' will be combined for the purpose of analysis. Moreover, all preferred terms from those two body systems that are subsequently listed in the same row will be combined:

- Red blood cell count decreased / Haemoglobin decreased / Haematocrit decreased / Mean cell volume decreased / Anaemia
- Fibrin D dimer increased / International normalised ratio increased / Prothrombin time shortened / Coagulopathy
- Eosinophil count increased / Eosinophilia
- Blood fibrinogen increased / Hyperfibrinogenaemia
- White blood cell count increased / Leukocytosis
- White blood cell count decreased / Leukopenia
- Lymphocyte count decreased / Natural killer cell count decreased / CD4 lymphocytes decreased / B-lymphocyte count decreased / Lymphopenia
- Monocyte count decreased / Monocytopenia
- Neutrophil count decreased / Neutropenia
- Neutrophil count increased / Neutrophilia
- Plasma cells increased / Plasmacytosis
- Platelet count decreased / Thrombocytopenia

TEAEs are defined as AEs occurring or worsening after the start (date and time) of the first study treatment (any IMP) and up to 28 days after the last study treatment including all treatment cycles (treatment emergent period). However, AEs occurring or worsening later than 28 days after the last treatment with study drug are defined as treatment emergent if these are considered to be related to the study drug.

If the start date and time of an AE are partially or completely missing, the AE will be assumed to be treatment-emergent if it cannot be definitely shown that the AE did not occur or worsen during the treatment-emergent period (worst case approach). Missing dates and times will not be replaced.

Thus, the following approach will be taken:

- If the start time of an AE is missing but the start date is complete, an AE will only be excluded from TEAEs if the start day is before the day of first treatment or the start day is after the end day of the treatment-emergent period.
- If the start time and day are missing but the start month is complete, an AE will only be excluded from TEAEs if the start month is before the month of first treatment or the start

month is after the end month of the treatment-emergent period or if stop date/time is before start of first treatment.

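### Protocol 12.1 ends AE recording at the earlier of EOS and 28 days after last dose, in conflict with the later AE assessments and the SAP's treatment-emergent window

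*Protocol*

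**What the plan says.** Protocol 12.1 has AEs and SAEs entered in the eCRF from informed consent to the EOS visit "or up to 28 days after the last administration of study medication, whichever is earlier", whether or not they are thought related.

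Other sections look beyond that point:

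- Protocol 10.1.12 requires "Toxicity/AE assessment since the last visit" at Follow-up Visit 2 and at each visit after it. On those further visits it says: "If there is still a response to therapy at this visit, then a follow-up visit will be repeated every fourth week".
- Protocol 11.3.1 has subjects observed and questioned for any kind of AE "at follow-up appointments throughout the study period with non-leading questioning".
- Protocol 11.3 states "All AEs and serious AEs (SAEs) will be recorded" and gives no end date.
- Protocol 7.1 sets the outer limit: "All subjects will be followed up for a maximum of 3 years after first administration of study drug".
- SAP 10.2 says that "AEs occurring or worsening later than 28 days after the last treatment with study drug are defined as treatment emergent" if they are considered related to study drug. It also flags AEs starting beyond the 28-day window as post-treatment, so it expects such records to exist.
- SAP 4.3 plans supplemental analyses of long-term safety follow-up.

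**The concern.** Incidence and severity of AEs is a primary endpoint (Protocol 11, SAP 2.2.1). A site that finds a new, drug-related AE at Follow-up Visit 2 is told by 10.1.12 to assess it and by 11.3 that it will be recorded. Under 12.1 the duty to record it has already ended. Sites may resolve this differently, and late related events would then reach the database for some subjects and not for others.

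The earlier-of rule has a second effect. If EOS is held before day 28, the recording duty stops at EOS. The SAP's treatment-emergent window, and the time at risk for its exposure-adjusted incidence rates, are still written to run to day 28.

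**Working it through.** The plan gives no figure on this point to reproduce. The check compares the timing rules.

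**1. Which limit operates.** Protocol 10.1.14 says: "The EOS visit will occur at least 28 days after last study drug administration but should be performed before any new MM therapy starts". EOS therefore normally falls on day 28 or later, and the earlier of the two limits is day 28. EOS is the operative limit only when new therapy brings it forward.

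**2. Where the follow-up visits fall** (days after last dose, from Protocol 10.1.12)

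- Visit 1: 28 ± 2, so days 26 to 30. It can already fall after the cut-off.
- Visit 2: Visit 1 plus 28 ± 2, so from 26 + 26 = 52 to 30 + 30 = 60. It is always after the cut-off, and the permitted two-week delay moves it later still.
- The interval that Visit 2 covers starts at Visit 1. At most two of its days (27 and 28, if Visit 1 was on day 26) lie inside the recording window.

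**3. Extent for one subject.** Assumptions: the subject stops without progression, keeps responding, starts no new therapy, and is followed to 3 years (1,095 days) after first dose with a visit every 28 days. With last dose on study day L, follow-up lasts 1,095 − (L − 1) days, of which 28 are inside the window.

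| Last dose (study day) | Days of follow-up | Days outside window | Visits after day 28 |
|---|---|---|---|
| 50 | 1,046 | 1,018 (97%) | 36 of 37 |
| 365 | 731 | 703 (96%) | 25 of 26 |
| 730 | 366 | 338 (92%) | 12 of 13 |

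These are the longest possible cases. Progression or new therapy ends follow-up sooner.

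**4. Early EOS.** If EOS is held d days after last dose, with d below 28, then 28 − d days of the SAP window have no recording duty. With d = 12 (assumed) this is 16 days. SAP 10.2 runs the time at risk of a subject without the event to as late as 28 days after last treatment, and makes no provision for an earlier EOS. For a subject treated for 50 days (assumed), time at risk is 50 + 28 = 78 days, and 16/78 = 21% of it falls after recording closed. As d goes from 1 to 27, the share goes from 27/78 = 35% to 1/78 = 1%. Such days add to the denominator of the rate when no event could have been entered under 12.1.

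**5. What still reaches the database after day 28**

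- Second primary malignancies, which 12.1 has reported for the duration of the study.
- AEs already recorded, which are followed to resolution or EOS with severity and relationship reassessed (Protocol 11.3.1, 12.1). Their later worsening is available to the SAP rule.

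This leaves new-onset related AEs after day 28, other than second primary malignancies, as the category without an assured source.

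**The case against.** The strongest reply is that 12.1 sets a duty to record up to a date and does not forbid recording afterwards. Where the same paragraph means exclusion it says so, as for non-serious AEs in screening failures. Its 24-hour reporting instruction for SAEs and AEs of special interest repeats no cut-off. Protocol 11.3 and 11.3.1 and the SAP's post-treatment flag all suggest that later AEs were expected. This stands. It means that late events are not certain to be lost; whether they are captured depends on which section a site follows.

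A reader might infer that the SAP's late-event rule has no data at all. The two routes in step 5 above show otherwise.

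A reader might also infer that every subject is affected. Follow-up visits apply only to those who stop for a reason other than progression (Protocol 7.1, 10.1.12), and repeat visits end at progression, new therapy or death. Subjects who progress go to EOS, and for most of them the ordinary 28-day window should be intact.

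A third tempting step is to take the 14-day half-life in Protocol 4.2 as a measure of the risk missed. That value belongs to one of two pre-trial simulation scenarios, both of which leave out the target-mediated sink. Residual drug is in any case not a count of unrecorded events.

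**Conclusion.** The point holds as an inconsistency between Protocol 12.1 on one side and Protocol 10.1.12, 11.3, 11.3.1 and SAP 10.2 on the other. Read literally, 12.1 largely removes the source for new-onset late related AEs in subjects who stop without progression. With an early EOS it also leaves part of the SAP's 28-day window uncovered.

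The likely direction is understatement of treatment-emergent incidence and of exposure-adjusted rates. The size cannot be derived: the documents do not say how many subjects stop without progression, how many have an early EOS, or how often late related AEs arise. The figures above describe visit timing and person-time under stated assumptions; they do not estimate missed events.

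The DLT and MTD determination is unaffected, because DLTs are confined to Cycle 1 (Protocol 8.5, SAP 10.1). A reader might suppose that the later of the two dates was intended in 12.1. Nothing in the documents says so, and they show only that the passages need to be reconciled.

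**What to change.** Amend Protocol 12.1 in two respects:

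- Record all AEs and SAEs for the full 28 days after last dose, not shortened by an early EOS.
- After day 28, record in the eCRF, through the EOS visit, those AEs and SAEs suspected to be related, as found at the follow-up visits already held. This matches SAP 10.2. Extending collection to all unrelated SAEs would go beyond what the SAP rule needs.

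An early EOS has no later scheduled visit, so one of two choices has to be written down: collect AEs to day 28 by a brief contact, or end the SAP's treatment-emergent window and time at risk at EOS for that subject. If the second is chosen, the 28-day wording in 12.1 needs the same exception.

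The cost is a protocol and SAP wording change, modest extra eCRF entry at visits where AEs are already asked about, and an occasional contact after an early EOS.
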